### ***Data analysis for Jacobi site***

Construction of epithelium maps by mLCI: Maps of the cervix delineating the T-zone will be created from each subject's mLCI data. The extent of columnar and squamous epithelia will be reported as a percentage of the image of the epithelium. Each scan in the 36 point field will initially be reviewed manually to determine the epithelium type based on the depth-resolved reflection profile for that point. The presence of clear histological layers is indicative of squamous epithelium while a thinner layer with less structure indicates columnar epithelium [22]. As we compile a database of mLCI maps of the cervix, we will develop automated algorithms for assessing epithelial types and transitions by using cluster analysis to discriminate scans. The mLCI maps will be compared to digital colposcopy analysis to assess accuracy.

Measurement of epithelial areas by colposcopy: Digital colposcopic images will be viewed in Adobe Photoshop for quantitative computerized planimetry as previously published [23, 24]. We will manually outline all areas of columnar, metaplastic and squamous epithelia and the total visible cervical face. Total pixel counts of the various epithelial types will be calculated and ectopy expressed as percentage of the total cervix.

Correlation of mLCI images to colposcopy and detailed written maps: The mLCI epithelial maps will be visually compared to colposcopic images to achieve co-registration. This is feasible based on the relatively modest number of patients in the study. The written map and white light imaging via the probe will aid in coregistration. We will correlate mLCI readings with calculated areas of epithelial types (pixel counts and percentage). Biostatistical analyses will address covariates including age, infections, cytology, menstrual cycle, and sexual behaviors.

Potential problems, alternative strategies, and benchmarks for success: The mLCI approach will be viewed as successful if there is less than average absolute difference of 10% in the area estimate compared with manual analysis.

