### **Design & Procedures**

#### **mLCI instrument**

The purpose of this instrument is to obtain optical measurements from the cervix via a vaginal probe to create a map of the surface cells that distinguishes the ectocervical and endocervical epithelia. The boundary between the two cell types is known as the squamocolumnar junction, or “t-zone”, which is the transitional region at which cervical dysplasia is most likely to occur.

The instrument delivers infrared light to 36 locations on the cervix, and measures the depth-profile of back-scattered light from each location using low coherence interferometry (LCI). This technique is thus termed multiplexed LCI (mLCI). The LCI profile data is stored by a computer for subsequent analysis to identify cell type.

The components of the mLCI instrument are grouped in the following modules: 1) Optical probe, 2) mLCI interferometer, 3) white light imaging module, 4) computer, and 5) physical enclosure.

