#### ***Optical Probe***

The optical probe is primarily cylindrical in form, with a diameter of approximately 25 mm and a rigid length of approximately 270 mm. The probe housing is fabricated by a 3D printing process known as fused deposition modeling (FDM). The material is MED-610 (Stratasys Inc., Eden Prairie, MN), a transparent polymer certified as biocompatible.

The adhesives used on the external seams of the probe are Silastic Medical Adhesive Type A (Dow Corning, Midland, MI), a soft silicone adhesive. A 36-channel single-mode fiber bundle is contained within the probe housing, as well as several glass optical elements for imaging. The rounded tip of the probe is intended to contact the cervical surface, and the focus of mLCI imaging is located on the plane of this tip.

The probe also contains fiber optics that deliver white LED illumination to the region of imaging and collects wide-field imaging information through a fiber bundle to provide real-time video endoscopic guidance for probe placement.

A flexible tether containing the 36-fiber bundle and white light optical fibers protrudes from the proximal end of the probe and is connected to the mLCI interferometer and white light imaging modules, respectively.

The full length of the probe is not intended for vaginal insertion. A demarcation line approximately 220 mm from the probe tip indicates the line beyond which the probe should not be inserted. High-level disinfection procedures as described in this document will be performed up to the line.

The probe contains no electrical components or wires.

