#### ***mLCI interferometer***

The centerpiece of LCI instrumentation is an interferometer, in which light from a known reference distance is combined with light returning from the probe. In our multiplexed design, 6 channels are simultaneously illuminated and interfered with each of 6 independent references. The mLCI thus contains 6 complete fiber optic interferometers, and fiber-optic switches redirect the optical inputs and outputs to progress through the 36 channels in a sequence of 6 acquisitions.

The 6 interferometers in the mLCI system are connected individually to each of 6 parallel fiber-optic spectrometers (Avantes, Broomfield, CO), which interface with the computer via one common USB connection.

The light source from the mLCI system is a superluminescent diode (Superlum, Moscow, Russia) emitting infrared light at wavelengths between 815 and 845 nm. The total output power of the SLD at its output aperture is less than 25 mW, but the amount of power delivered by the probe is far less. The power at each of the individual 36 foci at the probe output is less than 500  $\mu$ W (0.5 mW).

The maximum permissible exposure (MPE) for exposures greater than 10 seconds on skin is 3.6 mW/mm^2 at our principal wavelength of 830 nm (ANSI Z136.1). In our system, only 6 channels are simultaneously illuminated. Our imaging region in the tissue is 16 mm (defined by the length of our row of 6 spots) x 3.5 mm (defined by the minimum limiting aperture given in ANSI Z136.1) = 56 mm^2. Our total permissible power is thus 3.6 mW/mm^2 x 56 mm^2 = 201 mW. The totality of our 6 foci = 6 x 0.5 mW = 3 mW, which is far short of the ANSI MPE.

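### The 10% area benchmark sets 36 typed points against a continuous outline of the whole cervix, so it mixes typing error with sampling geometry that the plan leaves open

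*Combined protocol and SAP*

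**What the plan says.** The protocol section on the mLCI instrument states: "The instrument delivers infrared light to 36 locations on the cervix". The mLCI interferometer section lights six channels at a time, so that "fiber-optic switches redirect the optical inputs and outputs to progress through the 36 channels in a sequence of 6 acquisitions". Within its light-exposure calculation it gives the only dimension of the sampled pattern: "Our imaging region in the tissue is 16 mm (defined by the length of our row of 6 spots". The Optical Probe section describes a probe "with a diameter of approximately 25 mm".

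Under Data analysis for Jacobi site, the unit of reading is the point: "Each scan in the 36 point field will initially be reviewed manually to determine the epithelium type". A map showing the transformation zone is then drawn, and "The extent of columnar and squamous epithelia will be reported as a percentage of the image of the epithelium". The comparator is manual planimetry of colposcopic images: "Total pixel counts of the various epithelial types will be calculated and ectopy expressed as percentage of the total cervix". The criterion is: "The mLCI approach will be viewed as successful if there is less than average absolute difference of 10% in the area estimate", judged against manual analysis.

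The section does not say how 36 typed points become a percent area. It does not define the extent of the mLCI image or restrict the colposcopic percentage to the region that the probe sampled.

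**The concern.** The study asks whether mLCI can tell columnar from squamous epithelium. The success rule asks something broader: whether an area figure built from 36 points agrees with an area figure from a continuous outline over a different region. Two errors enter that difference. One is mistyping of points, which is a property of the device. The other comes from geometry: how points are turned into area, how coarse the grid is, and which denominator is used.

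If the geometric part is a sizeable fraction of 10 points, the benchmark says little about typing. Because the conversion rule and region are unstated, they could also be chosen after the data are seen, and that choice alone could move the average difference by several points.

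**Working it through.** **Inputs from the documents.** 36 points; 6 channels in each of 6 acquisitions; a row of 6 spots 16 mm long; probe diameter about 25 mm; benchmark 10%. The 10% has no derivation to reproduce. The one geometric product that can be checked does agree: 16 x 3.5 = 56 mm², as stated.

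**Assumptions.** An even 6 x 6 square grid (inferred; the row-to-row spacing is not given). A 16 x 16 mm square has a diagonal of 22.6 mm, so it fits the probe. The 10% is read as percentage points. Every point is typed correctly throughout, so all error below is geometric.

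**Step 1, spacing.** 16 / (6 - 1) = 3.2 mm.

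**Step 2, plain count against a 16 x 16 mm field.** Each point stands for 3.2² = 10.24 mm². The 36 points stand for 36 x 10.24 = 368.64 mm², while the field they bound is 256 mm². For a zone inside the field, averaged over placements, count share / true share = 256 / 368.64 = 25/36 = 0.694. The gap is the true share x 11/36.

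| True share of field | Gap, points | Simulated mean absolute error, points |
|---|---|---|
| 10% | 3.1 | 3.3 |
| 20% | 6.1 | 6.1 |
| 25% | 7.6 | 7.5 |
| 30% | 9.2 | 9.2 |
| 40% | 12.2 | 12.3 |

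The gap reaches 10 points at a true share of 32.7%. The simulation used round zones, 600 placements each, within 1.6 mm of centre. With elliptical zones (axis ratio 1 to 1.5), mean radius between 1 and 8 mm and centring SD of 0 to 2 mm, the scenario averages are 4.8 to 9.8 points.

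**Step 3, same typings, other conversions.**
- Edge weights (corners 1/4, edges 1/2, interior 1) on the 16 mm field: 2.4 to 3.0 points with round zones and 2.3 to 4.4 in the wider set; bias under 1 point.
- Interpolated (bilinear, thresholded) map on the 16 mm field: bias about -1.5 points, mean error 2.5 to 3.6.
- Plain count on a 19.2 mm frame (half a spacing beyond the outer points; 19.2² = 368.64 mm²): bias about nil, mean error 1.6 to 4.3.

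**Step 4, plain count against a total cervical face.** This is the denominator the plan names. Its size is not in the documents, so a range of diameters D is assumed. Ratio = (πD²/4) / 368.64.

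| D, mm | Face, mm² | Relative bias |
|---|---|---|
| 18 | 254 | -31% |
| 20 | 314 | -15% |
| 21.7 | 370 | about 0 |
| 25 | 491 | +33% |
| 30 | 707 | +92% |

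The low end keeps all 36 points in the denominator. On a centred 18 mm face the 12 outermost points (9.33 and 11.31 mm from centre) lie off the face. If they were dropped, 24 x 10.24 = 245.8 mm² against 254.5 mm² would give +3.5%. That is one more choice the plan leaves open.

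**Step 5, coarseness.** Any round zone centred on the grid with a radius between 2.26 and 5.06 mm covers the same 4 points and reads 4/36 = 11.1%, although its share of the 16 mm field runs from 6.3% to 31.4%.

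**Step 6, the same points for both methods.** If the colposcopic outline is read at the same 36 points, a correct reading with exact registration differs from it by zero, whatever the weights or region. What remains is typing plus registration error. With correct typing, an assumed registration SD of 1 mm per axis gives about 2 to 3 points on a plain count. At 2 mm with edge weights it is up to about 5.5 points.

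**The case against.** The strongest reply is that the plan specifies neither a plain count nor a 16 x 16 mm reference. It speaks of a map showing the transformation zone, which could be weighted or interpolated, and the 16 mm figure belongs to a light-exposure calculation. This stands. A reader might infer that mLCI under-reads columnar tissue by 30% under this plan. The documents do not support that: the bias is nearly nil on a 19.2 mm frame and changes sign for a cervical face wider than about 21.7 mm. For the same reason, one cannot say that over-calling columnar tissue would cancel the error and pass as accuracy.

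It is also fair that a perfect reader need not fail. The scenario averages in step 2 all stay below 10 points, and they rest on assumed zone sizes because the documents give no distribution of ectopy. Nor would a relative reading of the 10% make failure certain: under the better conversions the relative error is about 10% in some scenarios.

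Finally, this is early feasibility work, and visual co-registration adds error of its own to a point-by-point comparison. Both are true. They bear on how the result is labelled and how much weight the point deserves. They do not justify a benchmark whose geometric content is unknown.

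**Conclusion.** The concern holds in conditional form. The 10% criterion mixes typing error with geometry, and the plan does not fix the geometry. With every point typed correctly, the mean geometric error can be about 2 to 4 points (edge weights or a 19.2 mm frame) or 6 to 9 points (a plain count against a 16 x 16 mm field at true shares of 20% to 30%). Against an assumed cervical face of 18 to 30 mm, a plain count is biased by anything from about -31% to +92%. These figures rest on an inferred even 6 x 6 grid, assumed zone shapes and face sizes, and the 10% taken as percentage points. They show sensitivity to unstated choices and do not predict what this study will find. The change should be made because a more informative comparison is available from data already planned.

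**What to change.** In Data analysis for Jacobi site:

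1. After co-registration, overlay the same 36-point grid on each woman's colposcopic outline. Compare the mLCI percentage with this grid-sampled reference, so that both use the same points and region.
2. Report beside it the difference between the grid-sampled reference and the full outline (sampling error), and the full-area difference that the plan already names.
3. Where a percent area is reported from mLCI, weight each point by the tissue area it represents in the chosen region, or take the region as half a spacing beyond the outer points. State the choice before analysis.

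**Cost.** A few sentences and a short calculation on images and co-registrations already planned, with no new participants, readers or procedures.

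**Downside.** Co-registration is visual, so the grid comparison contains typing plus registration error (about 2 to 3 points at an assumed 1 mm SD, up to about 5.5 at 2 mm). It should be labelled that way and not presented as pure typing error.

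### The mLCI map is placed on the colposcopic image by comparing the two patterns, with no reading or placement fixed first, so measured agreement can be biased in the device's favour

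*Combined protocol and SAP*

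**What the plan says.** All of the following is in *Data analysis for Jacobi site* unless another section is named.

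- **Index reading.** "Each scan in the 36 point field will initially be reviewed manually to determine the epithelium type based on the depth-resolved reflection profile". The rule is qualitative: clear layering indicates squamous tissue, and a thinner, less structured layer indicates columnar. There is no numeric cut-off. Automated algorithms are to be developed later.
- **Reference reading.** "We will manually outline all areas of columnar, metaplastic and squamous epithelia and the total visible cervical face".
- **Alignment.** "The mLCI epithelial maps will be visually compared to colposcopic images to achieve co-registration". Then: "The written map and white light imaging via the probe will aid in coregistration".
- **Use.** "The mLCI maps will be compared to digital colposcopy analysis to assess accuracy". No location statistic is named.
- **Success rule.** "The mLCI approach will be viewed as successful if there is less than average absolute difference of 10% in the area estimate", the comparator being called manual analysis.
- **Bases of the two percentages.** For mLCI, "The extent of columnar and squamous epithelia will be reported as a percentage of the image of the epithelium"; for colposcopy, "ectopy expressed as percentage of the total cervix".

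*Multi-site Study: Responsibilities* has both sites' data analysed at Duke, with Jacobi data de-identified and a target of 40 completers. De-identification hides who the woman is, not what the other test showed. The weekly review under *Data accuracy and protocol compliance* concerns device operation. No section states an order of readings, masking of one reading from the other, or a point at which labels, outlines or placement are fixed.

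**The concern.** A comparison of an index test with a reference is informative only if neither reading, nor the link between them, is adjusted in the light of the other. Here the link is made by comparing the index result with the reference. Choosing the position and rotation at which two patterns look most alike produces agreement even when the index map carries no information.

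Two results are exposed, by different routes:

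1. **Location agreement**, such as where the squamocolumnar junction lies. *Purpose of the Study* makes this junction part of what the map should show. Pattern-matched placement can inflate it.
2. **The 10% area benchmark**, the only success rule stated for Jacobi. Placement hardly touches it, but a doubtful scan relabelled, or an outline redrawn, after the other reading is seen moves the area difference directly.

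**Working it through.** The plan gives no expected difference, standard deviation (SD) or power for the benchmark, so there is no figure of its own to reproduce. The calculations below test the mechanism.

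**Inputs from the documents.** 36 points (*mLCI instrument*); a row of 6 spots spanning 16 mm (*mLCI interferometer*), so spacing 16/5 = 3.2 mm if even; 40 women; limit 10%, read as percentage points. One point is 100/36 = 2.8 percentage points, so the limit equals 3.6 points. **Everything else is assumed:** a square 6 x 6 grid, the tissue pattern, point accuracy, search range and rate of revision.

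**1. Placement and location agreement.** Simulated elliptical columnar zone (semi-axes 3-9 mm, centre within 2 mm), 4,000 maps per setting. Agreement is the number of matching points divided by 36, at the true placement and at the best of 25 shifts (up to 3.2 mm each way) or of 75 placements (the same shifts with rotations of -30, 0 and +30 degrees).

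| Point accuracy | True placement | Best of 25 | Best of 75 |
|---|---|---|---|
| 50% (no information) | 50.1% | 60.5% | 62.5% |
| 60% | 60% | 66.5% | 68.3% |
| 70% | 70% | 73.4% | 74.9% |
| 80% | 80.1% | 81.4% | 82.3% |
| 90% | 90% | 90.3% | 90.7% |

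A second model allowed landmark error of up to 1.6 mm and 15 degrees, then searched 27 placements around the erroneous one, with 20-50% columnar tissue. Kappa was:

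| Point accuracy | True placement | Fixed on landmarks | Best match |
|---|---|---|---|
| No information | 0 | 0 | 0.18-0.26 |
| 60% | 0.11-0.20 | 0.09-0.15 | 0.23-0.34 |
| 70% | 0.25-0.40 | 0.19-0.31 | 0.33-0.46 |
| 80% | 0.43-0.60 | 0.32-0.46 | 0.48-0.60 |
| 90% | 0.67-0.80 | 0.51-0.63 | 0.67-0.77 |

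Both models show inflation for a weak device and little or none for a good one. In the second, landmark error pulls the fixed figure below the truth, and at 90% accuracy the matched figure can fall below it too.

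**2. Placement and area.** Whole-field percentages do not depend on placement. Within a registered footprint, the mean absolute difference went from 21.3 to 21.2 points (no information) and from 13.4 to 13.3 (70% accuracy) in the first model. In the second, best match differed from true placement by -0.4 to +0.8 points.

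**3. Revised readings and the benchmark.** For each woman, difference = 100 x |false columnar - false squamous| / 36. The benchmark is met if the mean over 40 women is below 10. Columnar share is beta-distributed with SD 12 points between women. Each discordant point is changed to agree with a stated probability.

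The result depends on how errors are shared. With the same error rate e in both tissues and columnar share p, the expected offset is e(1 - 2p):

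- 70% accuracy, p = 0.35: 0.3 x 0.30 = 9 points.
- 80% accuracy, p = 0.20: 0.2 x 0.60 = 12 points.

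With balanced errors the offset is zero. For 70% accuracy this means error rates of 0.15/0.65 = 0.23 in squamous and 0.15/0.35 = 0.43 in columnar tissue.

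| Case | Errors | Mean difference, saved readings | Chance of passing, saved readings | Chance with 30% re-read |
|---|---|---|---|---|
| 70% accurate, 35% columnar | equal rates | 11.9 | 7% | about 85% |
| same | balanced | about 9.5 | about 64% | over 99% |
| 80% accurate, 20% columnar | equal rates | 12.7 | 1% | about 81% |
| same | balanced | 8.3 | about 95% | little room to rise |

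In the first row, 10% and 20% re-reading give 23% and 53%. Under equal rates a 90%-accurate device passes either way, an 80%-accurate device at 35% columnar already passes 92% of the time, and a 70%-accurate device at 20% columnar fails either way. Judging against the continuous area rather than the same 36 points weakens the effect: with 30% re-reading, the equal-rate cases move from 9% to 76% and from 1% to 62%.

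**The case against.** **The text is partly protective.** Each scan is typed from its own depth profile, and the wording suggests that a map exists before co-registration. The white-light view shares the probe with the 36 fibres (*Optical Probe*) and is digitized (*White light imaging module*), so position could be set without the epithelial labels. This stands as far as it goes. The plan does not say that these aids are used first or alone, or that the readings are final once made.

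**A reader might infer that co-registration can carry a failing device past the 10% benchmark.** The documents do not support that: the benchmark concerns area, which placement barely changes. The benchmark's exposure comes from unsaved readings, a separate omission.

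**A reader might also infer that one person makes both readings, or that results will be biased.** The plan says only that analysis is at Duke. It does not say who reads what, and revision towards agreement is an assumption.

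**The comparator is ambiguous.** Manual analysis most likely means colposcopic planimetry, given the preceding text. But the scans are also reviewed manually, with automation to follow. If manual mLCI reading is meant, the outlines drop out of the benchmark and only the concern about labels remains.

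**This is preliminary work.** True, and no location threshold is stated. The plan nevertheless declares success on a numerical limit, and fixing the readings beforehand is cheap.

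**Conclusion.** The concern holds in limited form. The plan describes an alignment that uses the result under test and fixes no reading before comparison. This opens two possible routes to bias in the device's favour; neither is proven.

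- **Location:** inflation of about 10-12 percentage points in agreement, or about 0.2 in kappa, for an uninformative device; little or nothing at 90% accuracy. This affects the reported accuracy of the maps, not a stated threshold. A reader matching by eye may gain less than the best-match search used here.
- **Area benchmark:** revised readings could decide the result for a borderline device and would not change it for a clearly good one. The starting chance of passing at 70% accuracy and 35% columnar runs from 7% to about 64% on the error pattern alone, so none of these probabilities is an estimate for this study.

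The direction follows from the text. The sizes rest on assumed geometry, two tissue classes, one common denominator and one-way revision. The change should be made, but the gap does not invalidate the design.

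**What to change.** Amend *Data analysis for Jacobi site* to state this order:

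1. Label every scan from its depth profile and save the labels before that woman's colpophotograph is opened.
2. Draw and save the colposcopic outlines from coded images in a separate session, with the mLCI labels hidden. Different existing team members may do this if available; no extra reader is required.
3. Set and save position and rotation from the probe's white-light image and the written map, with the mLCI labels hidden. Only then overlay.
4. Compute the 10% benchmark from the saved readings, and say what manual analysis means. If location agreement is reported, name one statistic (for example, kappa over the 36 points), give it at the landmark placement, and show any pattern-matched figure beside it, labelled as such. If only area agreement is intended, say so.

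**Cost.** No extra visits or patients; the work is mainly reordered steps and saved files. One thing must be confirmed: *Study Procedures for subjects at Jacobi* lists no written-map step, and *Computer* mentions real-time display of white-light images without stating storage. If either is not kept for each woman, a recording step must be added.

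**Downside.** Some maps may not register on landmarks, and landmark error lowers the figure for a good device. At 90% accuracy and 35% columnar, the simulated loss of kappa is 0.08-0.11 with error up to 0.8 mm and 7.5 degrees, 0.15-0.22 at 1.6 mm and 15 degrees, and 0.30-0.41 at 3.2 mm and 30 degrees. Report the number of maps not registered, and call neither location figure the true value.

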## Purpose of the Study

The purpose of this study is to develop a multiplexed low coherence interferometry (mLCI) endoscopic probe for mapping the epithelial types of the cervix. This vaginal mLCI probe will obtain optical measurements from the cervix. These measurements can be used to create a map of the surface cells that distinguishes ectocervical epithelia, endocervical epithelia, and the squamocolumnar junction (t-zone) between them, which is the region where cervical dysplasia is most likely to occur.

The research study described here will be a preliminary study to evaluate the performance of the mLCI device for detection of cervical dysplasia. The results from a small study at Duke will help to optimize the function of the mLCI instrument before completing a larger study with collaborators at Jacobi Medical Center (see *Background & Significance* below). The device will be studied in a larger subject population at Jacobi to determine how effectively it can distinguish the types of cervical epithelia.

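### The only numerical success rule for the Jacobi cohort is an area difference, which carries no location, although the aim is a map of the epithelial types and their junction

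*Combined protocol and SAP*

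**What the plan says.** Purpose of the Study sets the aim as measurements that can "create a map of the surface cells that distinguishes ectocervical epithelia, endocervical epithelia, and the squamocolumnar junction (t-zone) between them". It gives the Jacobi cohort the task "to determine how effectively it can distinguish the types of cervical epithelia".

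Data analysis for Jacobi site then describes four steps:

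- **Maps.** "Maps of the cervix delineating the T-zone will be created" for each woman, and "Each scan in the 36 point field will initially be reviewed manually to determine the epithelium type". The columnar and squamous shares are reported as percentages of the mLCI image.
- **Reference.** Columnar, metaplastic and squamous areas are outlined by hand on digital colposcopy images. Ectopy is expressed as a percentage of the whole cervix.
- **Comparison.** "The mLCI maps will be compared to digital colposcopy analysis to assess accuracy". "The mLCI epithelial maps will be visually compared to colposcopic images to achieve co-registration". "The written map and white light imaging via the probe will aid in coregistration". mLCI readings are then correlated with the calculated areas.
- **Success.** The rule reads: "The mLCI approach will be viewed as successful if there is less than average absolute difference of 10% in the area estimate". Its yardstick is a manual analysis.

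No other numerical success criterion for Jacobi appears. The 10% precision under Data analysis for Duke site belongs to the 10-subject pilot there and does not concern map accuracy.

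**The concern.** The device is meant to show where each epithelial type lies and where the two meet. The success rule asks only how much of each type there is. Within a woman, a columnar point in the wrong place scores the same as one in the right place, and false-columnar points offset false-squamous points. The location-aware steps have no agreement measure that would reveal this.

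The rule is also loosely defined. It does not say which epithelial type it concerns, or whether 10% means percentage points or a relative difference. Manual analysis could mean the colposcopic outlines or the manual reading of the mLCI scans. The mLCI share and the colposcopic share are taken over different regions.

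At stake is the development milestone: a favourable result could be read as evidence that the map is right when that was not tested. This is early feasibility work, so no patient-care decision depends on the rule.

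**Working it through.** **Inputs from the documents.** 36 points per map (Data analysis for Jacobi site); 40 completing women (Multi-site Study: Responsibilities); a row of 6 spots 16 mm long (mLCI interferometer); margin 10%. The documents give no derivation for the margin, so there is no figure to reproduce. On a percentage-point reading, 10% of 36 is 3.6 points.

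**1. The area difference ignores location.** For one woman, on a common region,

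area difference = (false-columnar points − false-squamous points) / 36.

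Only the net count enters. Take 8 points truly columnar and 8 called columnar:

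expected agreement = (8×8 + 28×28) / 36² = 848 / 1,296 = 0.654

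kappa = (observed − 0.654) / (1 − 0.654)

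| Columnar points correctly placed | Points agreeing | Observed agreement | Kappa | Area difference |
|---|---|---|---|---|
| 0 of 8 | 20 of 36 | 0.556 | -0.29 | 0 |
| 4 of 8 | 28 of 36 | 0.778 | 0.36 | 0 |
| 8 of 8 | 36 of 36 | 1.000 | 1.00 | 0 |

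This illustrates the arithmetic and does not predict device behaviour. The offsetting is within a woman only; absolute differences do not cancel between women.

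**2. Different denominators.** Suppose the mLCI image covers a fraction f of the cervix and contains all the columnar tissue. If ectopy is c% of the cervix, a perfect mLCI map reports c/f %. The difference is c(1/f − 1), which is zero only if f = 1 or c = 0. It reaches 10 points at f = c/(c + 10): 0.50 for c = 10, 0.67 for c = 20 and 0.75 for c = 30. The documents give neither f nor c; these values of c are assumptions.

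**3. Would a non-discriminating device pass?** Assumptions: colposcopy as reference, percentage-point reading, 40 women, beta-distributed ectopy, each of 36 points called columnar at random at a fixed rate. Simulated share of cohorts with a mean absolute difference below 10 points:

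| Call rate | Ectopy mean/SD 8/8 | 10/10 | 15/12 | 20/15 | 30/20 |
|---|---|---|---|---|---|
| 10% | 99% | 90% | 45% | 2% | 0% |
| 15% | 42% | 36% | 37% | 5% | 0% |
| 20% | 0.1% | 0.3% | 6% | 2% | 0% |
| 30% | 0% | 0% | 0% | 0% | 0% |

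On a relative reading the rate is 0% throughout. The result depends on inputs that the documents do not give, so no single rate should be quoted.

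**4. What a location measure would face.** These simulations assume a 6×6 grid, a compact columnar patch whose centre varies between women, and the same five ectopy settings.

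- With a centre SD of 0.8 step, one fixed central map given to every woman has kappa 0.28 to 0.41, and the lower confidence limit is above 0 in every cohort. A kappa above 0 can therefore come from typical anatomy alone.
- Registering by the best of 9 one-step shifts lifts random 15% calls from kappa 0 to 0.12 to 0.19. Registration by pattern inflates agreement.
- Spacing along a row is 16 / 5 = 3.2 mm. Spacing between rows is not stated.

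**The case against.** The best defence is that the plan does not ignore location. It makes junction maps, types every point and co-registers each map with the colposcopic image, aided by the written map and the probe camera. A preliminary study may reasonably leave the accuracy comparison descriptive. This stands in part: a reader might infer that placement was overlooked, and the documents do not support that. But the comparison has no location statistic, and the only rule attached to the word success is an area.

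A second defence is that the area rule may well reject a useless device. This also stands. A reader might infer from the 99% above that such a device would probably pass, but the same table contains many zeros. The pass rate reflects the margin against the spread of ectopy, not misplacement. If manual analysis means the manual reading of mLCI scans, the rule benchmarks the automated algorithm and that table does not apply.

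A third objection concerns the remedy. It is tempting to require the device to beat the best fixed map as a pass/fail test. In simulation, a device with sensitivity 70% and specificity 90% meets such a test (interval above 0 and kappa above the fixed map chosen in hindsight) in 96–100% of cohorts when the centre SD is 0.8 step and registration is exact. The figure falls to 2–46% at 0.4 step and 0–15% at 0.2 step. At 0.4 step with a registration error of 0.25 step it is 0–2%. The documents give neither quantity, so the test could fail an informative device. The objection is upheld, and no such threshold is proposed.

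**Conclusion.** The point holds. That an area difference carries no location follows from its definition and needs no assumption about the device. Under the rule as written, maps with kappa from -0.29 to 1.00 can all score an area difference of 0, so meeting it would not show that the device places the epithelial types or the junction. The unequal denominators are a separate flaw in the rule: a correct map can show a difference unless both percentages cover the same region.

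The documents do not support saying that the plan has no spatial analysis, that a non-discriminating device would be likely to pass, or that patient care is at risk. The harm is limited to a misleading milestone in early feasibility work. The change should be made before the mLCI calls are compared with colposcopy.

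**What to change.** **Area rule.** Keep it. Compute both percentages over the same co-registered region. State the epithelial type, whether 10% is percentage points or relative, and, if that is what is meant, that manual analysis is the colposcopic planimetry.

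**Location measure.** Prespecify one and report it beside the area rule: columnar-versus-squamous kappa, with sensitivity and specificity, at the co-registered points, with 95% intervals bootstrapped by woman. Take expected agreement from each woman's own counts and pool as Σ(observed − expected) / Σ(1 − expected), so that getting the amount right without the place earns no credit. Show results with and without metaplastic areas, which colposcopy outlines but the two-type reading of the mLCI profiles does not describe.

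**Benchmark.** Report the kappa of one fixed map given to every woman, descriptively. Do not make beating it a pass/fail test.

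**Registration.** Where possible, register from the written map and the probe white-light image before the mLCI calls are seen. If the mLCI pattern is used, say so and note that it inflates agreement.

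**Conclusion.** From the area rule alone, claim area agreement, not localisation.

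**Cost.** About 40 × 36 = 1,440 points to score, and no extra visit. The written map and white-light images must be kept: Study Procedures for subjects at Jacobi names only colpophotographs, and although the white light imaging module digitises the image, the Computer section describes a real-time display. Registration error will lower kappa, and its size is unknown. The junction is resolved only to the point spacing, about 3.2 mm along a row.
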